## Methodology

### Participants

Participants will be identified at the Brain and Cognition Discovery Foundation (BCDF). Twenty subjects with obesity, will be enrolled. All patients will be assessed for concurrent psychiatric disorders (e.g. mood disorders). Eligibility criteria are as follows: inclusion criteria: (a) 18-65 years of age; (b) meeting DSM-V criteria for: (i) major depressive disorder (symptomatic or asymptomatic in any phase of the illness) or (ii) bipolar disorder I/II (symptomatic or asymptomatic in any phase of the illness); (c) ability to provide written and informed consent; (d) obesity 30 kg/m^2; (e ) weight under 440lbs; (f) shoulder-to-shoulder width under 60 cm; Exclusion criteria are as follows: (a) age below 18 or above 65; (b) use of benzodiazepines or consumption of alcohol within 12 hours of assessments; (c) abuse of marijuana; (d) physical,

cognitive, or language impairments sufficient to adversely affect data derived from assessments; (e) diagnosed reading disability or dyslexia; (f) clinically significant learning disorder by history; (g) history of moderate or severe traumatic brain injury; (h) other neurological disorders, or unstable systemic medical diseases; and (i) pregnancy and post-partum period (j) presence of any contra-indications for MRI; (k) weight above 440lbs; (l) shoulder-to-shoulder width greater than 60 cm. All subjects will be consented prior to initiating the study; (m) >45 BMI; (n) suicidality as determined by clinical discretion.

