### **Statistical Analysis**

Graph theoretical analysis (GTA) will be used to assess functional connectivity of the default mode network, cognitive control network, affect network and reward network. This is a

preliminary exploratory analysis, descriptive statistics will be conducted on the sociodemographic, clinical and metabolic parameters. Associations between obesity and alterations in functional connectivity will be the primary outcome of interest and additional coprimary outcome is the association between obesity and reward motivation as indexed by the EEfRT/MID/PRT task. Laboratory parameters will be used to explore potential mediational relationships between obesity and brain connectivity measurements, as well as reward performance.

For each variable, distribution normality will be assessed with one-sample Kolmogorov-Smirnov tests. Comparisons between groups will be conducted using independent samples t-tests and Mann-Whitney U (for normally and non-normally distributed variables, respectively). Participants are given 20 minutes to complete the EEfRT, and the number of trials completed during that time will vary among them (Table 1). Consistently with previous studies, only the first 50 trials will be used. Similar to previous studies using the EEfRT, we will use generalized estimating equation (GEE) models to test the effects of groups, reward magnitude and probability on the willingness to expend effort for rewards (i.e. percentage of trials on which the 'hard' task was selected). We will use an independent matrix, which best fit our data, and a binary logistic distribution to model the dichotomous outcome of choosing the hard versus the easy task. All GEE models will include reward magnitude, probability, and expected value (EV, defined as the interaction between reward probability and magnitude). In addition, each model will include a trial number as a covariate to control for possible effects of fatigue over the course of the task. Reward magnitude will be categorized in three groups: low (<\$2.30), medium (\$2.31-\$3.29), and high (>\$3.30). To assess associations between EEfRT and clinical and metabolic data, we will calculate the mean proportions of hard-task choices for all subjects.

Stepwise linear regression will then be used to identify significant predictors. MRI/DTI will be attained for all subjects.

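### The analysis tests undefined groups in a sample where everyone has obesity, and names no obesity exposure for the co-primary questions

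*Combined protocol and SAP*

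**What the plan says.** The Study Synopsis gives the primary aim as whether obesity goes with poorer performance on the reward and motivation tasks. The Statistical Analysis section sets two primary questions: "Associations between obesity and alterations in functional connectivity will be the primary outcome of interest", and an additional "coprimary outcome is the association between obesity and reward motivation as indexed by the EEfRT/MID/PRT task".

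The sample is a single set of people. Under Participants, "Twenty subjects with obesity, will be enrolled". The eligibility list gives a BMI of 30 as the obesity criterion and excludes BMI above 45. Every participant must also have MDD or bipolar disorder. No section describes people without obesity.

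The planned tests are these:

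- "Comparisons between groups will be conducted using independent samples t-tests and Mann-Whitney U", the choice depending on normality.
- A GEE on hard versus easy choices in the EEfRT, "to test the effects of groups, reward magnitude and probability on the willingness to expend effort for rewards". The other listed terms are expected value and trial number.
- A per-person EEfRT summary: "To assess associations between EEfRT and clinical and metabolic data, we will calculate the mean proportions of hard-task choices for all subjects".
- A variable-selection step, whose candidate variables are not listed: "Stepwise linear regression will then be used to identify significant predictors".
- A mediation analysis: "Laboratory parameters will be used to explore potential mediational relationships between obesity and brain connectivity measurements, as well as reward performance".

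BMI has a formula in the Primary and Secondary Outcome Measures section but no role in any analysis. That section also words the primary outcome as an association among the three tasks, with no obesity term. It makes connectivity secondary, whereas the Statistical Analysis section makes it primary.

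**The concern.** The tests compare groups, but the design has only one group with respect to the exposure of interest. The only groups given levels in the Statistical Analysis section are the low, medium and high reward magnitudes, which classify trials and not participants.

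An analyst following the section must therefore invent either the participant groups or the obesity variable for the primary question, and could do so after seeing the data. Calling the study a preliminary pilot excuses low power. It does not remove the need for a named exposure and an estimate with an interval.

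The conclusion is also at stake. The Implications section expects to attribute reward disturbances to obesity. A sample with no one below the obesity threshold cannot support a statement about obesity versus none, or about overweight.

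**Working it through.** The plan states no alpha, power, effect size or sample-size derivation, so there is no figure to reproduce. The check takes each possible meaning of the group term in turn.

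**Inputs from the documents.** 20 participants, all with obesity; BMI from 30 to 45 (Introduction and Participants); first 50 EEfRT trials per person; GEE with logit link and independence working matrix; terms for magnitude (three categories), probability, expected value and trial number (Statistical Analysis).

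**Assumptions, not in the documents.** Two-sided alpha 0.05; 80% power; BMI uniform on 30 to 45; a linear relation; random-intercept SDs of 0.7 and 1.2 for the GEE simulation.

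**1. Obese versus non-obese.** The two-sample standard error is proportional to √(1/n₁ + 1/n₀). With n₁ = 20 and n₀ = 0, the term 1/0 is undefined. In the GEE the columns are intercept, obesity, probability, medium magnitude, high magnitude, expected value and trial number: 7 columns. Obesity equals 1 for everyone and so duplicates the intercept. The rank is 6 of 7 and the obesity effect is not estimable. This needs no distributional assumption.

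**2. MDD versus bipolar disorder.** Estimable if both diagnoses are enrolled, but it does not test obesity.

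**3. BMI split within the 20.** Estimable, but no cut-off is given. To show what the choice would cost, power from 100,000 simulated samples of 20:

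| True r | Continuous BMI | 10:10 split | 15:5 split |
|---|---|---|---|
| 0.3 | 25.5% | 19.0% | 15.0% |
| 0.5 | 65.5% | 48.9% | 36.2% |
| 0.59 | 83.6% | 66.2% | 50.6% |

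**4. Continuous BMI.** Replacing the indicator with BMI gives rank 7 of 7, so the effect is estimable. Precision at n = 20:

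- Critical r: t(18, 0.975) = 2.101, so 2.101/√(18 + 2.101²) = 0.444.
- Detectable r at 80% power by Fisher's z: tanh((1.960 + 0.842)/√17) = tanh(0.680) = 0.59. The table shows 83.6% at this value because it uses a t-test with uniform BMI. The Fisher approximation is slightly conservative here.
- 95% CI for an observed r of 0.3: tanh(0.3095 ± 1.96/√17) = tanh(0.3095 ± 0.4754) = −0.16 to 0.66.

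**5. GEE variance with 20 clusters.** With no true BMI effect, 4,000 runs per SD and about 36 to 37% hard choices, rejection at a nominal 5% was:

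| Test | SD 0.7 | SD 1.2 |
|---|---|---|
| Usual sandwich, z | 9.6% | 9.6% |
| Mancl-DeRouen, z | 5.8% | 5.6% |
| Mancl-DeRouen, t(18) | 4.6% | 3.9% |

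Simulation standard error near 5% is √(0.05 × 0.95/4000) = 0.3 points.

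**6. Do the other planned lines supply the exposure?**

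- The regression line covers the EEfRT against clinical and metabolic data. It does not list BMI, and it covers neither MID, PRT nor connectivity.
- Stepwise selection could drop BMI even if it were a candidate, leaving no estimate for the primary question.
- The laboratory mediation line is the only analysis line that links obesity to connectivity. It gives no model and no obesity measure.

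**The case against.** The strongest reply is that a BMI gradient was intended all along. The Introduction describes adults across a range of BMI above 30 and speaks of a correlation with effort, and the BMI formula follows directly after the primary outcome. On that reading the question is answerable and the plan is merely under-specified. This is the most natural reading. But it is an intention in the Introduction, and no sentence in the Statistical Analysis section carries it into a model.

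Three points about the figures are fair. The plan proposes no BMI split, so the power lost by splitting shows the cost of one way of filling the gap and is not an error in the plan. The small-cluster problem applies to any between-person term in this GEE, however the groups are resolved, and its size rests on assumed SDs. The mismatch in the primary outcome and the overweight wording are separate inconsistencies, though they add to the uncertainty about what is being tested.

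It is also fair that naming BMI does not finish the job: the connectivity metric and the MID and PRT summary scores are not named either.

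The study calls itself a pilot and an exploratory analysis. That lowers what may be claimed, but declared co-primary outcomes still need an exposure.

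**Conclusion.** The concern holds and should be fixed before analysis. As written, the group tests either cannot estimate an obesity effect (20 versus 0; rank 6 of 7) or test something else, and no model guarantees an estimate for either co-primary question. This rests on the documents alone.

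With BMI as a continuous exposure the question becomes answerable in a narrower form: degree of obesity among adults with MDD or bipolar disorder. A detectable correlation of about 0.59 shows how little precision 20 people give; it depends on the assumed alpha and power. The near doubling of the GEE error rate (9.6% against 5%) depends on the assumed SDs and BMI distribution.

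**What to change.** In the Statistical Analysis section:

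- **EEfRT.** Replace the group term in the GEE with continuous BMI, forced into the model. Use a bias-corrected sandwich variance (for example Mancl-DeRouen) with a t reference, because there are only 20 clusters.
- **MID, PRT and connectivity.** For each measure, report the association with BMI and a 95% CI. Choose either a regression slope or a Spearman correlation for each outcome in advance. Name the MID and PRT summary scores and the connectivity metrics at the same time.
- **Stepwise regression.** Do not let it determine whether the BMI association is reported.
- **Mediation.** Name BMI as the obesity measure.
- **t-test and Mann-Whitney line.** Define the participant groups and label the comparison descriptive (for example MDD versus bipolar disorder), or remove the line.

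Elsewhere, restate the aim and conclusion as the association of higher BMI with reward performance and connectivity among adults with MDD or bipolar disorder and BMI of about 30 to 45. Align the overweight wording with the eligibility criteria. Make the Primary and Secondary Outcome Measures section agree with the Synopsis and the Statistical Analysis section.

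The cost is wording plus a standard small-sample GEE option. BMI is already collected, so no participants, procedures or eligibility criteria change. The price is a narrower claim with limited precision. Keeping the obese versus non-obese question would need a comparator without obesity, which changes eligibility and recruitment and is not costed here.

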## Study Synopsis:

Anhedonia and abnormalities in reward behavior are core features of overweight/obesity (OW), a highly prevalent condition within MDD populations and is independently associated with reward disturbances. We therefore aimed to investigate the brain substrates subserving reward and motivation in adults with overweight/obesity. Herein, we are primarily interested in three overlapping, yet distinct aspects, of anhedonia. We are primarily interested in motivation, reward valuation, and reward learning towards addressing the measurement of each of these respective subdomains, eligible participants will complete validated gold standard measures (i.e. the Effort Expenditure for Rewards Task (EEfRT) (reward valuation), Probabilistic Reward Task (PRT) (reward learning), and the Monetary Incentive Delay (MID) task (reward anticipation)).

Twenty adults with overweight/obesity will complete all tasks at a single visit with two of the tasks being completed prior to MRI and one of the tasks (i.e. EEfRT) will be completed during MRI acquisition.

The **primary aim** of this pilot study is to determine whether associations exist between obesity and decreased performance on the respective motivation/reward paradigms. In addition, associations between performance on reward tasks and functional connectivity, as measured by MRI and DTI, a secondary objective is to ascertain whether associations exist between performance on the motivation reward tasks and gold standard measures of food intake (i.e. food diary) and energy expenditure (i.e. calorimetry).

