Within MDD populations, obesity, and its metabolic correlates (e.g. insulin resistance), have been associated with increased self-reported anhedonia. As a result, anhedonia has been proposed as a key clinical mediator between MDD and metabolic comorbidities.

Nevertheless, few studies have used objective methods to assess reward deficits in populations with MDD and obesity. Herein, we aim to explore the role of OW in effort-based decision making in overweight/obese adults with varying levels of body mass index (BMI) above 30kg/m^2. We primarily aim to investigate the effects of OW correlation with effort for rewards, as measured by the Effort Expenditure for Rewards Task (EEfRT). The secondary aim is to examine the associations between effort-based decision-making as measured by EEfRT, with MRI/DTI measured alterations in reciprocity between reward and cognitive control circuits.

We **hypothesize** that obesity is associated with deficits in each of the reward paradigms we have selected. We also **hypothesize** that the foregoing disturbances correlate with functional disconnectivity within reward/cognitive control networks.

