## Effort Expenditure for Rewards Task (EEfRT), Probabilistic Rewards Task (PRT), and Monetary Incentive Delay (MID) task

The EEfRT measures participants' willingness to make efforts to obtain a monetary reward under different conditions of reward probability and magnitude. In each EEfRT trial, participants are given an opportunity to choose between two tasks with different levels of difficulty: "hard task" and "easy task." Successful completion of the easy task trials requires 30 button presses using the dominant index finger within 7 seconds, whereas the hard task trials requires 100 button presses using the non-dominant little finger within 21 seconds. Participants will be informed that successful trial completion does not guarantee winning the monetary reward. Before making a choice, participants are provided with information that varies from trial to trial regarding: (1) the probability (12%, 50%, or 88%) of winning the money; and (2) the magnitude of reward for successfully completing the hard task. The reward magnitude will be set at \$1.00 for easy tasks and higher amounts that will vary per trial within a range of \$1.24-\$4.30 for hard tasks. Probability levels will always be applied to both the hard task and easy task, and there will be equal proportions of each probability level across the experiment. Participants are given 20 minutes to perform the task; thus, the number of trials will vary across the participants. The Probabilistic Rewards Task (PRT) measures response bias and sensitivity to reward under variable conditions. The Monetary Incentive Delay (MID) task assesses the basis of anticipation and consumption of reward and punishment. Each test takes approximately 20 minutes to administer.

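### The obesity–EEfRT association has no single prespecified test, and the GEE that tests an undefined 'groups' term has only 20 clusters and no stated small-sample correction

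*Combined protocol and SAP*

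**What the plan says.** Statistical Analysis makes the link between obesity and reward motivation, indexed by EEfRT, MID and PRT, a coprimary outcome. The Study Synopsis gives a similar aim: the purpose "of this pilot study is to determine whether associations exist between obesity and decreased performance" on the reward tasks.

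For EEfRT, Statistical Analysis states "we will use generalized estimating equation (GEE) models to test the effects of groups, reward magnitude and probability" on willingness to choose the hard task. It continues: "We will use an independent matrix, which best fit our data, and a binary logistic distribution to model the dichotomous outcome". Only the first 50 trials are used. Every model also carries expected value (EV, the magnitude-by-probability interaction) and trial number. The task description says "thus, the number of trials will vary across the participants", so some people may contribute fewer than 50.

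The same section plans other comparisons by group: "Comparisons between groups will be conducted using independent samples t-tests and Mann-Whitney U". For clinical and metabolic associations it plans each participant's mean proportion of hard choices, then stepwise linear regression.

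On the sample, Participants says "Twenty subjects with obesity, will be enrolled". Eligible diagnoses are "i) major depressive disorder (symptomatic or asymptomatic in any phase of the illness) or (ii) bipolar disorder I/II". The Introduction speaks of "overweight/obese adults with varying levels of body mass index (BMI) above" 30 kg/m², and Participants excludes BMI over 45.

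The plan names no variance estimator, reference distribution, significance level or small-sample correction.

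**The concern.** There are two linked gaps.

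- **The test is not identified.** Everyone enrolled has obesity, so 'groups' cannot mean obese versus non-obese. It could mean major depression versus bipolar disorder, or bands of BMI, and these answer different questions. BMI appears in neither the GEE description nor the regression sentence. The regression route is stepwise, so the final model depends on the data. A reader cannot tell which p-value answers the coprimary question.
- **The GEE inference is not specified where it matters.** Repeated choices by one person are correlated. An independence working matrix is acceptable, but valid standard errors then need a robust (sandwich) variance, which is too small when clusters are few. The number of clusters here is 20 however many trials each person completes. The bias is worst for a term that varies only between people, such as a group or BMI.

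At stake are nominal 5% results with a higher real error rate, and intervals that are too short.

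**Working it through.** The plan gives no significance level, power or sample-size figure, so there is nothing of its own to reproduce.

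**Inputs from the document:** 20 participants; at most 50 trials each; probability 12%, 50% or 88%; hard-task reward $1.24–$4.30 in three categories; EV and trial number as covariates; BMI between 30 and 45.

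**Assumed, because not stated:** two-sided 5%; uncorrected sandwich with |z| > 1.96; the group split; the BMI shape; between-person spread on the logit scale.

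**Step 1: exact check on 20 person means, 10/10 split.** The uncorrected sandwich divides by n where the unbiased variance divides by n − 1. It is therefore 9/10 of the right size, and the test rejects when |t₁₈| > 1.96 × √0.9 = 1.859. The probability is 7.9%, not 5%.

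**Step 2: why imbalance makes it worse.** For groups of size a and b, the expected uncorrected variance is proportional to (a−1)/a² + (b−1)/b², against a true 1/a + 1/b.

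- 10/10: 0.180 / 0.200 = 0.90
- 14/6: 0.205 / 0.238 = 0.86
- 16/4: 0.246 / 0.3125 = 0.79

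**Step 3: simulation of the described logistic GEE under no person-level effect.** Each setting had 5,000 runs of 20 people × 50 trials, with random-intercept SD 0.5, 1.0 and 1.5. Monte Carlo standard error was about 0.3–0.65 points.

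| Term | Uncorrected z | Mancl–DeRouen, t(18) |
|---|---|---|
| 10/10 | 7.2–7.7% | 3.5–3.6% |
| 14/6 | 8.5–9.5% | 4.0–4.7% |
| BMI uniform 30–45 | 9.0–9.7% | 4.1–4.7% |
| BMI right-skewed | 11.4–12.4% | 4.9–5.5% |
| 16/4 | 12.3–14.0% | 5.4–6.9% |
| 17/3 | 17.6–18.4% | 7.8–8.7% |
| 18/2 | 27.6–29.9% | 13.4–14.4% |
| Within-person terms | 6.5–8.0% | 3.9–4.8% |

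One prespecified linear regression of the per-person proportion gave 4.0–5.7% across the person-level settings. That figure does not cover the planned stepwise selection.

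**Step 4: sensitivity.** A separately written simulation with other coefficients gave 7.5–10.3% (10/10 and 14/6), 7.8–9.9% (even BMI), 12.7–14.3% (16/4) and 11.7–13.8% (skewed BMI). With a lower hard-choice rate the upper ends reached about 11% (10/10 to 14/6 splits, even or uniform BMI) and 15.6% (16/4). It put the corrected 16/4 test at about 6–8%. Between-person spread mattered little. With 16 people analysed, the uncorrected rates were 11.4% (uniform BMI) and 13.5% (skewed).

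**Step 5: price of the correction.** On person means the Mancl–DeRouen variance is proportional to 1/(a−1) + 1/(b−1), and t(18) replaces 1.96 with 2.101, a factor of 1.072. Interval widths grow as follows.

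- 10/10: √(0.2222/0.180) × 1.072 = 1.19
- 14/6: √(0.2769/0.2052) × 1.072 = 1.25
- 16/4: √(0.400/0.2461) × 1.072 = 1.37

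This agrees with the simulated widening of about 20%, 25% and 37%.

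**The case against.** The strongest reply is that the percentages describe a test the plan never states. A reader might infer that the sponsor has chosen an uncorrected z-test, or from the words about an independent matrix that all choices will be treated as independent observations. The document supports neither: it is silent on the variance. The rates are conditional.

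A reader might also infer that the coprimary obesity test itself has a 7–14% error rate. That goes too far. The more natural reading sends EEfRT associations with clinical and metabolic data through per-person proportions, not the GEE. On that reading the person-level inflation does not touch the obesity question. The problem there is stepwise selection, whose error rate is not quantified here.

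The term 'groups' may also be carried over from an earlier comparative study. The working matrix is described as having already fitted the data best, and the Implications section reports findings in an MDD subgroup. If so, the group comparison may never be run. That is a reason to delete or define the term.

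Finally, the primary outcome is worded inconsistently. Primary and Secondary Outcome Measures names the association among the three tasks without mentioning obesity, and Statistical Analysis puts connectivity first. The obesity–reward aim still appears in the Synopsis, the Introduction and as a coprimary outcome. The exploratory label also stands and limits the consequence, but the plan still speaks of testing effects and finding significant predictors.

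**Conclusion.** The point holds as an under-specified analysis with a measurable risk, not as a stated error. From the text alone: 20 clusters, no obesity contrast, 'groups' undefined, BMI not named in the GEE, a stepwise route to the clinical associations, and no variance method or significance level. The coprimary obesity–EEfRT association therefore lacks one valid prespecified test.

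The size rests on an assumed two-sided 5% level and an uncorrected sandwich z-test. It is about 7–10% for balanced to 14/6 splits or evenly spread BMI, about 11–14% for a 16/4 split or skewed BMI, and about 6.5–8% for within-person terms. The splits and BMI shapes are assumptions, and these ranges are not upper bounds. With no decision rule attached, the harm is over-reading of pilot results. It is worth correcting before analysis.

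**What to change.** Make one clear change to Statistical Analysis:

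1. State that the obesity–EEfRT test is one prespecified linear regression of each participant's hard-choice proportion on continuous BMI, without stepwise selection, and give the significance level and sidedness.
2. Delete 'groups' from the GEE, or define it and label it exploratory.
3. Keep the GEE for magnitude, probability, EV and trial number, with the independence matrix, a Mancl–DeRouen bias-corrected sandwich and a t reference on participants analysed minus 2 degrees of freedom. Apply the same correction to any person-level term that is kept.
4. Report a very unbalanced group split descriptively, because the corrected test stays inflated there (about 8–9% at 17/3 and 13–14% at 18/2).

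The cost is a few sentences and a variance option, with no new data. GEE intervals for a person-level term become about 20–37% wider. The per-person regression needs no special software. At assumed BMI effects of 0.5, 0.7 and 0.9 logit per SD with uniform BMI, its power was 50%, 79% and 95%, against 44%, 72% and 91% for the corrected GEE.

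Its limit should be stated. If between-person spread tripled from lowest to highest BMI, its error was 4.4% with uniform BMI but 12.4% with skewed BMI, against 4.0% and 8.8% for the corrected GEE. The spread of proportions against BMI should therefore be inspected and reported.

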In humans, insulin resistance is associated with less endogenous dopamine at D2/3 receptors in the ventral striatum and nucleus accumbens, in both obese and non-obese adults. Another study documented that weight loss following bariatric surgery was associated with an increase in D2 receptor availability. In effort-based decision-making, evidence indicates that dopamine responsivity, particularly in the striatum and ventromedial prefrontal cortex, is strongest for low probability trials. Conversely, we observed a stronger effect of overweight/obesity in the low reward trials. If overweight/obesity and the peripheral measures of insulin resistance used herein do indeed reflect and/or are associated with brain insulin resistance, it could be posited that disturbances in central insulin signaling lead to decreased dopamine sensitivity, resulting in an increased likelihood to choose low-effort options. This hypothesis, however, has two principle outstanding questions. First, it relies on the assumption that peripheral and brain insulin sensitivity are correlated (or that peripheral measures are reliable indicators of central processes), which is insufficiently characterized. Direct measurements of brain insulin sensitivity, and its relationship to dopamine signaling and effort-based decision-making, are necessary.

Second, it assumes that disturbances in insulin signaling are the principle mediators of the changes in dopamine function; an idea that does have support in the literature, but cannot be fully ascertained in a cross-sectional study. Moreover, recent evidence has indicated that the brain is also as an important regulator of systemic glucose and energy metabolism. For example, bromocriptine, a potent dopamine D2 receptor agonist, has been shown to improve glucose metabolism in humans. Dopamine release in the striatum might enhance whole-body insulin sensitivity, whereas inhibition of dopamine activity might reduce it. Therefore, individuals predisposed to lower central dopamine activity may be more susceptible to the development of obesity and insulin resistance states. Disturbances in reward behavior,

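### The EEfRT model has no term for obesity or BMI changing the response to reward, so the plan tests overall willingness to work but not sensitivity to reward value

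*Combined protocol and SAP*

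**What the plan says.** The Study Synopsis assigns reward valuation to the EEfRT. The task description says it measures "willingness to make efforts to obtain a monetary reward under different conditions of reward probability and magnitude", so probability and amount are varied by design from trial to trial.

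The Statistical Analysis section uses GEE with "a binary logistic distribution to model the dichotomous outcome of choosing the hard versus the easy task", to "test the effects of groups, reward magnitude and probability on the willingness to expend effort for rewards". All models include magnitude, probability and "expected value (EV, defined as the interaction between reward probability and magnitude", and "each model will include a trial number as a covariate to control for possible effects of fatigue". It adds that "Reward magnitude will be categorized in three groups". Only the first 50 trials per person are used.

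Clinical and metabolic associations are a separate step, in which "we will calculate the mean proportions of hard-task choices for all subjects", followed by stepwise linear regression.

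The Implications section, discussing effort-based decisions and dopamine, reports that "we observed a stronger effect of overweight/obesity in the low reward trials".

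**The concern.** The model has one interaction, between two features of the trial (probability and magnitude). No term lets the person-level exposure, whether called group, obesity or BMI, modify the effect of magnitude or probability. The exposure can therefore only shift the overall log-odds of choosing the hard task. The mean proportion used for the clinical and metabolic associations has the same limit, because it averages over all reward conditions.

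Two different findings are then hard to separate. People with higher BMI may choose the hard task less often whatever is on offer, or their choices may depend differently on what is on offer. The planned exposure term addresses the first. The second is an exposure-by-reward interaction, and an obesity effect that is larger in low-reward trials is of that kind. If such an effect exists and roughly cancels over the reward range, the planned analysis would report no association. If an overall difference is found, the plan does not say whether it depends on reward. The EEfRT carries the main behavioural aim in the Introduction, so this bears on a central result.

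**Working it through.** **Terms in the plan.** Exposure (groups), magnitude, probability, probability × magnitude, trial number. Interactions named: one. Interactions involving the exposure: none. Analyses of the exposure within a magnitude band: none.

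**Can the data support such a term?** Hard-task amounts run from $1.24 to $4.30 and the low band ends at $2.30. If amounts are uniform over the range (an assumption), the low band holds (2.30 − 1.24)/(4.30 − 1.24) = 1.06/3.06 = 0.346 of trials, or 0.346 × 50 ≈ 17 per person. The contrast is available in data already planned.

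**No figure to reproduce.** The sample of 20 is given without alpha, power or effect size. Two-sided 0.05 is assumed below. For scale, a correlation of BMI with the mean hard-choice proportion has 80% power only at |r| = tanh[(1.960 + 0.842)/√17] ≈ 0.59.

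**Simulation set-up.** 20 people, 50 trials each, BMI spread over 30–45 (Participants section: obesity at 30 kg/m², exclusion above 45), independence logistic GEE, bias-corrected sandwich errors, t on 18 df. BMI takes the place of groups. Effect sizes, baseline coefficients and variance components are all assumptions; none comes from the documents.

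*Design 1: BMI acts only on the magnitude slope.* Person-intercept SD is 1.0 and residual slope SD 0.4 logit, with 400 to 600 studies per scenario. A slope effect b (logit per SD of BMI per SD of magnitude) implies a BMI–slope correlation r = b/√(b² + 0.4²).

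| b | implied r | BMI × magnitude rejects |
|---|---|---|
| 0 | 0 | 4% |
| 0.1 | 0.24 | 12% |
| 0.126 | 0.30 | 14% |
| 0.2 | 0.45 | 26–29% |
| 0.3 | 0.60 | 54–57% |
| 0.4 | 0.71 | 77–79% |
| 0.5 | 0.78 | 93–94% |

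Ranges are separate runs of the same design. At b = 0.3 to 0.5 the BMI main effect and the mean-proportion correlation reject in about 5–6%, which is chance.

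With a main effect also present the order reverses. At −0.5 logit per SD of BMI plus b = 0.126, the main effect rejects in 43% and the interaction in 13%; at −0.8 plus b = 0.126, 81% and 13%. With a uniform shift of −0.5 alone, 42% and 4%.

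*Design 2: BMI effect in low-reward trials.* Person-intercept SD is 0.8, with 600 studies per scenario and effects in logits per SD of BMI.

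| Scenario | BMI main effect | Mean proportion | BMI × low reward |
|---|---|---|---|
| Null | 3.8% | 3.5% | 4.3% |
| Uniform −0.3 | 29.2% | 30.5% | 5.3% |
| Low-reward trials only, −0.8 | 13.3% | 15.0% | 92.5% |
| +0.25 overall, −0.8 added in low-reward trials | 4.0% | 4.3% | 91.8% |

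The last two rows follow from averaging. An effect of −0.8 in about 35% of trials is roughly 0.346 × (−0.8) = −0.28 logit per trial, and adding +0.25 leaves about −0.03.

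**The case against.** Several stronger readings are tempting, and the documents do not support them.

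- A reader might infer that the models contain main effects only. They do not: expected value is an explicit probability × magnitude interaction in every model. What is absent is an interaction with the exposure.
- A reader might infer that the GEE is itself reduced to a mean proportion. It stays a trial-level binary model; the mean is a separate step for clinical and metabolic associations.
- A reader might conclude that the plan cannot show anything about reward valuation. The Introduction counts willingness to work for an outcome as part of valuation and describes the obesity deficit as reduced willingness to invest effort. A main effect speaks to that directly.
- A reader might treat the low-reward result as a hypothesis the study undertakes to re-test. It is reported as something already observed, in a discussion section, and no aim, hypothesis or outcome commits to re-testing it. A stronger effect at low reward may also come with an overall effect that the planned model could detect.
- A reader might take an interaction to be free of person-level confounding because it is a within-person contrast. Depression severity or medication could alter reward sensitivity too.

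The power figures also need care. Design 1 is a pure crossover, which is neither the low-reward pattern nor the general deficit that is hypothesised, and its favourable results need BMI–slope correlations of 0.60 to 0.78. At more modest slopes the power is poor. The analysis is described as preliminary and exploratory, and extra tests in 20 people add multiplicity.

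These points limit the claim to what is not tested, and they rule out replacing the main effect. They do not supply the missing term: the three magnitude bands are defined, but no exposure-by-band comparison is named.

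**Conclusion.** The point stands in limited form. As written, the plan tests whether obesity goes with lower overall willingness to expend effort; it does not test whether obesity changes the response to reward magnitude or probability. That rests on reading the listed model terms and needs no simulation.

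The practical size depends on the true pattern, which the documents do not give. For a pure slope effect, interaction power runs from about 12–29% at 0.1–0.2 logit to about 54–94% at 0.3–0.5 logit; at the larger slopes a main-effect test finds it only at chance. For a uniform shift the main effect is clearly better (29% against 5%, or 42% against 4%). The upper figures should not be read as the expected gain.

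A more basic gap lies underneath. All 20 participants are obese, so the groups term has no contrast, and an interaction cannot be specified until the exposure is defined. Defining it would not by itself add the missing term. This is a cheap improvement to an exploratory analysis and does not invalidate the planned one.

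**What to change.** In the Statistical Analysis section:

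1. Replace groups in the EEfRT GEE with continuous BMI, and keep its main effect as the test of overall willingness.
2. Add BMI × reward magnitude, with magnitude in dollars, and BMI × probability. Label both as prespecified and exploratory.
3. Report all three BMI terms as estimates with confidence intervals, using small-sample-corrected sandwich errors because there are only 20 clusters.
4. State that the interactions supplement the main effect and that a non-significant interaction at this sample size is not evidence of no difference in reward sensitivity.

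The mean hard-choice proportion can stay as the summary for clinical and metabolic associations. Carrying individual slopes into those analyses is not recommended here, since each would rest on at most 50 binary choices and would multiply the tests.

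The cost is SAP wording and two model terms, with no new data or participant burden. The downside is two more exploratory tests, with low power unless the effect is large.
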